- a) Primary Outcome
 - a) Outcome Measure Title: Reduction in severity of CINV
 - b) Outcome Measure Description: Assessed by the mean score of the Antiemesis (MAT) tool, which measures acute and delayed CINV across patients' chemotherapy regimens.
 - c) **Outcome Measure Timeframe**: Data tool collected during study visits 1, 2, 3, and 4.
- b) Secondary Outcome
 - a) Outcome Measure Title: Reduction in Antiemetic Use
 - b) **Outcome Measure Description**: Assessed by the mean score of antiemetics diary, which measures the usage frequency (date and time) and type (name) of antiemetic medications.
 - c) **Outcome Measure Timeframe**: Data diary collected during study visits 1, 2, 3, and 4.
- c) Exploratory Outcome
 - a) Outcome Measure Title: Improved Resilience
 - b) **Outcome Measure Description**: Assessed by the mean score of the Connor-Davidson Resilience Scale (CD-RISC), which measures the participants' resilience pre and post the intervention.
 - c) Outcome Measure Timeframe: Data collected at baseline and final visit.
- d) Exploratory Outcome
 - a) Outcome Measure Title: Reduction in Psychological Distress Symptoms
 - b) **Outcome Measure Description**: Assessed by the mean score of the psychological distress symptoms visual analog scale the patients' anxiety, stress, and depression at pre-and post-assessment.
 - c) Outcome Measure Timeframe: Data collected at baseline and final visit.
- e) Exploratory Outcome
 - a) Outcome Measure Title: Improved Quality of Life
 - b) **Outcome Measure Description**: Assessed by the mean score of Functional Assessment of Chronic Illness Therapy General (FACIT-G), which measures the

patients' quality of life and well-being at pre-and post-assessment.

c) Outcome Measure Timeframe: Data collected at baseline and final visit.

The study objectives and endpoints were selected because (a) more research is necessary to understand the effects of aromatherapy on moderate and high emetogenic chemotherapy regimens in an outpatient setting; (b) the literature suggests that CINV has a relationship with decreased quality of life and increased antiemetic usage and psychological distress symptoms; (c) the relationship between CINV and resilience has not been established. However, literature has shown a relationship between resilience and a reduction in psychological distress symptoms and improved quality of life.

9) Procedures Involved*

The study will continue as follows:

Initial visit

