The study's initial visit will occur while patients are in the CTU or fast-track area as they get ready for treatment. The entire study will be explained to the patient when they are preparing for their chemotherapy regimen in a comfortable area provided by the SCCC. After answering the potential participants' questions, the study team member will go through the study's informed consent process if the participant is interested and willing to consent. The potential participants will have time to review and discuss informed consent. After the patient signs the informed consent, the participant will be randomized to the control or the intervention arm.

On the same day, the study team member will meet the participant in the CTU while they receive their infusion and provide both the control and intervention groups, access to complete, via iPad or laptop, the electronic pre-assessment and demographic form, psychological distress VAS, resilience scale, FACIT-G, and a study packet that includes the Antiemesis (MAT) tool, antiemetic diary or antiemetic/aromatherapy diary. The study packet will be completed and returned to the study team member on the participants' next scheduled chemotherapy infusion. The study team member will explain to the participants how to use the MAT tool and how to fill the antiemetic diary or antiemetic/aromatherapy diary. The study team member will go through the instructions to ensure that they understand the forms and how to complete them.

Arm 1 - Control group:

Participants in the control group will receive standard medical care, consisting of antiemetic medicine at the first sign of CINV on a schedule as prescribed by the healthcare provider. The study team member will review with the participant how to use the weekly study packet (e.g., MAT tool and antiemetic diary) and explain that a study team member will collect the packet on their next scheduled chemotherapy infusion.

Arm 2 - Intervention group:

Participants in the intervention group will receive an aromatherapy inhaler for complementary use with their antiemetic medication. Participants will be encouraged to use the aromatherapy inhaler at the first sign of CINV before taking their antiemetic medications that are labeled "as needed". The interventional group will be instructed that one normal inhale is equivalent to one dose of aromatherapy and must report essential oils sensitivity to a study team

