member. The participant will be withdrawn from the study if essential oils sensitivity is identified. Aromatherapy will be used as often as needed or whenever CINV is encountered. Participants are advised to take their prescribed antiemetic medications that are labeled "as needed" as directed by their healthcare provider if they find insufficient comfort change in their CINV after using the aromatherapy. The study team member will explain to the participants that they will need to fill out the MAT tool and antiemetic/aromatherapy diary. And study team member will collect the packet on their next scheduled chemotherapy infusion.

Visit 1: Participants' visit one will take place on their next scheduled chemotherapy infusion – i.e., the participants' first chemotherapy cycle during their study period.

Arm 1 - Control group:

A study team member and participant will meet during the participant's scheduled CTU appointment to collect their MAT tool and antiemetic diary. During this interaction, the study team member will reinforce instructions and answer any participant's questions, concerns, or confusion regarding the MAT tool and antiemetic diary. A new study packet will be provided to the participants.

Arm 2 - Interventional group:

A study team member and participant will meet during the participant's scheduled CTU appointment to collect their MAT tool and antiemetic/aromatherapy diary. During this interaction, the study team member will reinforce instructions and answer any participant's questions, concerns, or confusion regarding the aromatherapy inhaler, MAT tool, and antiemetic/aromatherapy diary. A new study packet and an aromatherapy inhaler, if necessary, will be provided to the participants.

Visit 2: Participants' visit two will take place on their next scheduled chemotherapy infusion – i.e., the participants' second chemotherapy cycle during their study period.

Arm 1 - Control group:

A study team member and participant will meet during the participant's scheduled CTU appointment to collect their MAT tool and antiemetic diary. During this interaction, the study team member will reinforce instructions and answer any participant's questions, concerns, or confusion regarding the MAT tool and antiemetic diary. A new study packet will be provided to the participants.

Arm 2 - Interventional group:

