The participants will complete a pre-assessment and demographic checklist that assesses their demographic information (e.g., race, ethnicity, age, and education level), essential oils sensitivity, and risk factors of CINV. The pre-assessment demographic checklist will provide the descriptive characteristics of the study's sample population.

• Additional data, such as medical history (e.g., diagnoses, allergies, medications, cancer history, and treatment regimen), family history, and recent outpatient and inpatient clinic or hospital visits, will be extracted from the electronic health record.

Aromatherapy Inhaler (Arm 2 – Intervention Only):

The study's aromatherapy inhaler can be used when participants' have their first sign of CINV and as needed. The aromatherapy inhaler contains a proprietary blend of peppermint, spearmint, lavender, and ginger essential oils that can last up to 6 months. Participants will twist open the cap, hold the inhaler below their nose, and take deep breaths to activate the aromatherapy inhaler. Once the participant is done, they will close the aromatherapy inhaler to turn it off. The aromatherapy vapors can be safely inhaled for as long as it takes to provide comfort and relief for the patient. There are no "limits" or duration restrictions for any essential oils in the blend. The aromatherapy inhalation amount can vary from brief intermittent use to continuous inhalation over several minutes. The aromatherapy inhaler has unlimited uses with no time limits. One inhalation of aromatherapy is equivalent to one dose. There are no known contraindications. At each study visit, the study team member will offer the participant a replacement aromatherapy inhalation device.

Antiemetic/Aromatherapy Diary (Arm 2 - Intervention Only):

The antiemetic/aromatherapy diary will allow the participants to record their weekly usage (date and time) of aromatherapy and antiemetic uses and evaluate the aromatherapy and type (name) of antiemetic medications. The evaluation will assess the effects of the aromatherapy on CINV by capturing the number of inhalations per nausea episode and asking the participants, 'Did the aromatherapy take away your nausea?' answers include: 'it took away my nausea completely' to 'it had no effect on my nausea.' If the participants cannot get relief from the aromatherapy, the participants will take the prescribed antiemetic, and the participants will document the type of antiemetic medication they needed.

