Additionally, there is a space to name other complementary methods used to relieve CINV and describe how the CINV was controlled in the antiemetic/aromatherapy diary.

MAT Tool:

The Antiemesis (MAT) tool created by the Multinational Association of Supportive Care in Cancer (Dranisaris et al., 2017) is a user-friendly and reliable tool designed to measure acute and delayed CINV across patients entire chemotherapy regimen. The MAT tool is available in English and Spanish languages. The MAT tool consists of eight items that assess participants' CINV (i.e., occurrence, duration, and frequency). Four items assess the participants' acute phase (i.e., first 24 hours after receiving chemotherapy), and the last four items assess the delayed phase (i.e., day 2 to day 4 after chemotherapy treatment). The MAT tool has been used as a communication tool to facilitate discussions about their CINV to their healthcare providers (Alafafsheh & Ahmad, 2016; Molassiotis et al., 2007; Yamaguchi et al., 2009). This MAT tool has shown good reliability and validity, with Cronbach alpha of 0.77-0.97 in 1200 patients with cancer (Alafafsheh & Ahmad, 2016; Dranisaris et al., 2017; Molassiotis et al., 2007; Yamaguchi et al., 2009).

Antiemetic Diary (Arm 1 - Control Only):

The antiemetic diary allows the participants to record their usage (date and time) and type (name) of antiemetic medications. Additionally, there is a space to name other

complementary methods used to relieve CINV and describe how the CINV was controlled in the antiemetic diary.

Resilience Scale:

The Connor-Davidson Resilience Scale (CD-RISC) will assess the participants' resilience pre and post the intervention (Burns & Anstey, 2010). For this study, we will use the 10-item questionnaire that includes questions such as: are you 'able to adapt to change,' 'can (you) deal with whatever comes,' to 'can handle unpleasant feelings.' This scale has shown good reliability and validity, with Cronbach alpha of 0.88 in 343 patients with cancer and 122 breast patients with cancer (Matzka, Mayer, Köck-Hódi, Moses-Passini, Dubey, Jahn, ... & Eicher, 2016; Scali, Gandubert, Ritchie, Soulier, Ancelin, Chaudieu, & Uddin, 2012).

Psychological Distress Symptoms:

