All endpoints will be evaluated using parametric analysis to examine the difference between the two conditions across the 3-time points for primary endpoints (CINV and Use of Antiemetics) and 2-time points for secondary endpoints (resilience, psychological distress, and quality of life). The analysis will be conducted using SPSS Version 26. For binary outcomes (CINV), logistic regression will be used. For continuous outcomes (antiemetic use, resilience, psychological distress, and quality of life) a Mixed ANOVA will be used with condition as the between-subjects variable and change over time on the outcome as the within-subjects variable. Sphericity and homogeneity of variance assumptions will be tested prior to interpretation of the results, and the

Greenhouse-Geisser correction will be implemented if Sphericity is violated. A type I error rate of .05 will be used to determine significance for all analyses.

Outcome	Measure	Type of measurement
CINV	MAT	Binary
Use of antiemetics	Antiemetic Diary	Continuous
Resilience	CD-RISC	Continuous
Psychological Distress	Visual Analog Scale	Continuous
Quality of Life	FACIT-G	Continuous

2. Analysis of the Primary Endpoint(s)

For CINV, logistic regression will be used to determine whether the use of aromatherapy decreases the risk for any of the following outcomes: acute nausea, delayed nausea, acute vomiting, or delated vomiting. For use of antiemetic medication, a Mixed ANOVA will be used to evaluate differences between conditions (aromatherapy group vs. treatment as usual) across the 3-time points (Visit 1, Visit 2, and Visit 3). Time x treatment effects will be evaluated as well as main effects.

3. Analysis of the Secondary Endpoint(s)

For resilience, psychological distress, and quality of life, a Mixed ANOVA will be used to evaluate differences between conditions (aromatherapy group vs. treatment as usual) across the 2-time points (Initial visit and final visit). Time x treatment effects will be evaluated as well as main effects

4. Baseline Descriptive Statistics

Participant demographic characteristics will be analyzed using descriptive statistics. Specifically, frequencies and percentages will be reported for categorical variables, and means and standard deviations will be reported for continuous variables.

12) **Provisions to Monitor the Data to Ensure the Safety of Subjects***

This section is not applicable. The risks of this study are minimal.

13) Withdrawal of Subjects*

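### The primary nausea analysis scores occurrence, so it gives no credit for relief from an inhaler that is used in response to symptoms

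*Combined protocol and SAP*

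**What the plan says.** **How the inhaler is used.** Section 9 (Procedures Involved) gives three instructions, and each is tied to symptoms:

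- Arm 2, at the initial visit: "Participants will be encouraged to use the aromatherapy inhaler at the first sign of CINV before taking their antiemetic medications" that are labelled for use as needed.
- Later in the same instructions: "Aromatherapy will be used as often as needed or whenever CINV is encountered".
- In the inhaler description: "The study's aromatherapy inhaler can be used when participants' have their first sign of CINV and as needed".

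No scheduled or pre-emptive use is described.

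**How nausea is analysed.** Section 11, General Approach, states: "For binary outcomes (CINV), logistic regression will be used". The table there lists the MAT as a binary measure. Part 2 adds that "logistic regression will be used to determine whether the use of aromatherapy decreases the risk for any of the following outcomes: acute nausea, delayed nausea", then names acute and delayed vomiting. It gives no severity threshold, no duration and no category for relieved nausea.

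**What the trial sets out to show.** Hypothesis 1(a) in Section 3 is about less discomfort from CINV. The Study Endpoints section titles the primary outcome "Reduction in severity of CINV" and measures it by the mean MAT score.

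**What is collected.** Section 9 says: "The MAT tool consists of eight items that assess participants' CINV (i.e., occurrence, duration, and frequency"), with four items for the first 24 hours and four for days 2 to 4. Relief is asked about in the intervention arm's diary, where "answers include: 'it took away my nausea completely' to 'it had no effect on my nausea". The control arm's diary has no such item.

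**The concern.** A treatment taken once a symptom has begun can shorten or ease that episode, but it cannot stop the episode from having begun. If the outcome is whether nausea occurred in the phase, the episode that prompts the first inhalation already settles the answer. A participant whose every episode was fully relieved and one who got no relief both score as having had nausea.

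A null result on acute or delayed nausea occurrence could then be read as evidence that aromatherapy does not help nausea, even if it relieved nausea well. Section 4 reports that patients rank nausea above vomiting as the worst side effect, so this is an important part of the primary question. No other planned between-arm analysis measures relief: the diary item exists in one arm only, and antiemetic use is a separate aim.

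The point is linked to the conflict between Study Endpoints (severity, mean score) and Section 11 (binary), but it adds something. Settling that conflict in favour of the binary outcome would make the documents agree and still leave a nausea test that cannot register relief. It is therefore a reason to settle the conflict in the other direction.

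**Working it through.** The plan gives N = 100 with no power calculation, effect size, event rate or allocation ratio, so there is no figure of its own to reproduce. The main argument comes from reading the sections together; the numbers only illustrate it.

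**Inputs.** From the documents: N = 100 (Section 6); type I error 0.05 (Section 11); 40% CINV in moderate to high emetogenic chemotherapy and 71% nausea in patients with breast cancer (Section 4). Assumed: 50 per arm; two-sided test; one cycle; no dropout; a third nausea rate of 85%, because Section 5 requires earlier nausea or vomiting; log-normal nausea duration, median 6 h in control and 3 h with the inhaler; log SD 0.8 or 1.2; the same proportion p with nausea in both arms.

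**Step 1: occurrence.** With relief but no prevention, P(nausea) = p in both arms. The null hypothesis is then true for occurrence, and the test rejects at its type I error, about 5%, however large the relief. This follows from the assumption of equal occurrence; it is not an empirical finding.

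**Step 2: a graded measure.** Score duration, with 0 for no nausea. The probability that a control participant scores worse than an inhaler participant, counting ties as half, is

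θ = ½ + p² × [Φ(ln 2 / (σ√2)) − ½].

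- σ = 0.8: ln 2 / (0.8 × 1.414) = 0.613, Φ = 0.730, bracket = 0.230.
- σ = 1.2: ln 2 / (1.2 × 1.414) = 0.408, Φ = 0.658, bracket = 0.158.

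Power of the Mann-Whitney test is by simulation (at least 4,000 trials per scenario).

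| Nausea rate p | p² | θ (σ 0.8) | Rank test (σ 0.8) | θ (σ 1.2) | Rank test (σ 1.2) | Occurrence test |
|---|---|---|---|---|---|---|
| 40% | 0.160 | 0.537 | about 10% | 0.525 | about 8% | about 5% |
| 71% | 0.504 | 0.616 | about 53% | 0.580 | about 28% | about 5% |
| 85% | 0.723 | 0.666 | about 82% | 0.615 | 48–51% | about 5% |

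The gain depends on p², so it is small at 40% nausea and substantial at 71% or above.

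**Step 3: relaxing equal occurrence.** If the inhaler also cuts occurrence by 10% in relative terms, with duration halved and σ = 0.8, occurrence against rank test is 12% against 71% (p = 71%) and 18% against 93% (p = 85%). If occurrence falls by 30%, the occurrence test alone reaches about 58% and 83%.

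**Step 4: what an occurrence test needs.** With n = 50 per arm,

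power = Φ{[p₁ − p₂ − 1.96√(2p̄(1−p̄)/n)] / √([p₁(1−p₁) + p₂(1−p₂)]/n)}.

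For p₁ = 0.71 and p₂ = 0.436: p̄ = 0.573, so (0.274 − 1.96 × 0.0989) / 0.0951 = 0.84 and power is 80%. The same calculation gives 40% to about 15%, and 85% to about 60%. The inhaler would have to prevent nausea altogether in about 25 to 27 of every 100 participants.

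**The case against.** The strongest reply is that timing rules out an effect on occurrence only for the first episode in a phase.

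- The MAT scores the acute and delayed phases separately, so inhaler use in the first 24 hours comes before any delayed-phase nausea.
- Participants keep the inhaler across three collection periods, so use in one cycle comes before nausea in the next.
- Section 4 cites literature that aromatherapy may prevent CINV as well as reduce it, and Section 9 also allows use as needed.
- Vomiting can plausibly be averted after nausea starts.

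All of this stands. A reader might infer that the whole primary analysis is bound to be null, or that the trial cannot answer its first aim. The documents do not support that: two of the four outcomes are vomiting, and delayed or later-cycle nausea could respond. Nor do they say that the inhaler may be used only after nausea has begun; they describe symptom-triggered use and no scheduled use.

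Two further objections also hold. The power gain is fragile, as the 40% row and the log SD of 1.2 show. And Section 9 does not say which MAT items grade nausea rather than vomiting, so the availability of a nausea duration item is not established. Finally, part 2 can be read as four separate outcomes, so the concern about a composite applies only if a composite is intended.

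None of this gives credit for relief of the triggering episode, which is the effect that hypothesis 1(a) describes.

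**Conclusion.** The concern holds in a limited form. The planned nausea comparison is insensitive to relief of the episode that prompts inhaler use, and relief is what hypothesis 1(a) and the severity endpoint set out to test. The trial is not blind to every effect: vomiting, delayed nausea and later-cycle nausea could still show a difference.

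The reading rests on the documents alone. Its size does not: equal occurrence, 1:1 allocation, halved duration, log SD and the 85% rate are assumptions. Within them, a graded measure ranges from little better than the occurrence test (8–10% against 5% at 40% nausea) to much better (about 82% against 5% at 85% nausea with log SD 0.8). The 5% should not be quoted as the trial's actual power for nausea, because it follows from assuming no prevention.

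**What to change.** In Section 11, part 2, bring the analysis into line with the Study Endpoints section:

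- Make the primary nausea comparison a graded MAT measure for each phase, with 0 for no nausea. Name the item: whichever of nausea extent, duration or frequency the MAT records.
- Compare it between arms over Visits 1 to 3 with a method suited to a skewed outcome with many zeros, such as a rank-based or two-part analysis that allows for repeated cycles.
- Keep logistic regression for acute and delayed vomiting.
- Keep nausea occurrence as a supportive between-arm analysis, since delayed or later-cycle onset might respond.
- Do not use a composite of any CINV as primary, because one brief, relieved episode of nausea would count as an event.
- Amend the General Approach table, which lists the MAT only as binary.

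The diary relief question cannot replace this, because the control arm does not answer it.

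The cost is a change of analysis wording, provided that the MAT has a graded nausea item; the sponsor should confirm this from the instrument. No change to visits or inhaler use is involved. The downside is an effect measure less simple to report than an odds ratio.

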> chemotherapy without utilizing antiemetic medications (Eghbali et al., 2017; Herz, 2005; Hodge, McCarthy, & Pierce, 2014). Similar to aromatherapy, resilience, a person's ability to cope positively and adapt to their cancer diagnosis and treatment has shown to reduce symptoms such as anxiety and depression and increase the patient's well-being (Matzka et al., 2016). This study aims to investigate the effect of aromatherapy inhalation as a complimentary nonpharmaceutical intervention on CINV, resilience, and the use of antiemetics among patients with cancer receiving moderate to high emetogenic chemotherapy regimens outpatient. The study team used the National Comprehensive Cancer Network (NCCN) guidelines (NCCN,2020) to identify moderate and high emetogenic chemotherapy regimens.

5) Inclusion and Exclusion Criteria*

Inclusion includes:

- 18 years of age or older
- able to read and speak English or Spanish
- able to and willing to give informed consent
- currently undergoing moderate and high emetogenic chemotherapy (adjuvant or neoadjuvant)
- receiving three or more remaining cycles of chemotherapy
- symptoms of nausea or vomiting after the first chemotherapy infusion

Exclusion includes:

- unable or unwilling to give informed consent
- sensitivity to essential oils*
- olfactory disorders
- receiving chemotherapy for the first time
- undergoing low emetogenic chemotherapy regimens
- patients with hormone-sensitive cancers
- timely request of treating provider
- presently participating in an ongoing research study

(*) sensitivity to essential oils will be assessed when the study team members screen and recruit a potential participant.

6) Number of Subjects*

The total single-site sample size is 100.

7) Study-Wide Recruitment Methods*

Not applicable, for study's single site recruitment methods see section #24.

8) Study Timelines*

This research study can feasibly be completed in a proposed two-year time frame.

The duration period per participant will vary depending on their prescribed chemotherapy regimen, ranging from four to 12 weeks. If a participant is admitted to an SCCC's inpatient unit or has their chemotherapy temporally held during their study period, the study procedures will be postponed until their next scheduled outpatient CTU visit, see Table 1. The study will recruit 100 patients from a wide variety of racial and ethnic groups, gender, and over the age of 18.

Table 1. Participant Study Duration

Study Endpoints*

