The Study's intervention group uses an aromatherapy inhaler, leading to a potential sensitivity to essential oils. Participants will be informed that in the case they have a sensitivity to essential oils, they need to stop using the inhaler and contact the Study PI immediately. The participant will be withdrawn from the Study and encouraged to see their healthcare provider.

There are no foreseeable participant risks or inconveniences related to participation in the research. The participants are free to withdraw at any time, and their decision to participate, refuse, or withdraw will have no impact on their treatment or any other relationship with SCCC. There is no economic burden for the participants.

The participant will be considered "lost to follow-up" if they stop communicating with the study team. The participant will also be considered "lost

to follow-up" if the participant's oncologist withdraws them from IV moderate to high emetogenic chemotherapy.

14) **Risks to Subjects***

Quality assurance will follow the University of Miami School of Nursing and Health Sciences quality assurance guidelines. These include minimizing potential harm for the participants.

The study measures include questions regarding well-being, some of which may cause emotional distress or discomfort. Participants will be informed that they may refuse to answer any question if they do not feel comfortable answering it. If a participant expresses or demonstrates emotional distress, the participant will be encouraged to contact the Sylvester Comprehensive Cancer Center (SCCC) Cancer Support Services for an appointment at [contact] or [contact].

The study's intervention group uses an aromatherapy inhaler, leading to a potential sensitivity to essential oils. Participants will be informed that in the case they have a sensitivity to essential oils, they need to immediately stop using the inhaler and contact the PI of the study, [name]. The participant will be withdrawn from the study and encouraged to see their healthcare provider.

There are no foreseeable participant risks or inconveniences related to participation in the research. The participants are free to withdraw at any time, and their decision to participate, refuse, or withdraw will have no impact on their treatment or any other relationship with SCCC. There is no economic burden for the participants.

Unanticipated Problems (Adverse Events and Serious Adverse Events) a) Definition of Unanticipated Problems

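### The repeated-measures Mixed ANOVA for antiemetic use drops every participant who lacks one of the three diaries; a linear mixed model would keep anyone with at least one

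*Combined protocol and SAP*

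**What the plan says.** Section 11 (Data Management), under General Approach, states for the continuous outcomes that "a Mixed ANOVA will be used with condition as the between-subjects variable and change over time on the outcome as the within-subjects variable". It adds that "Sphericity and homogeneity of variance assumptions will be tested prior to interpretation of the results", that the "Greenhouse-Geisser correction will be implemented if Sphericity is violated", and that "The analysis will be conducted using SPSS Version 26". Under Analysis of the Primary Endpoint(s), it applies this to antiemetic use: "a Mixed ANOVA will be used to evaluate differences between conditions (aromatherapy group vs. treatment as usual) across the 3-time points", namely Visits 1, 2 and 3.

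The supplied text has no imputation rule, no defined analysis set and no allowance for dropout. Missing data come up once, in section 11, as something the team reviews in weekly contact with the principal investigator.

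Section 9 (Procedures) sends the diary home in a packet that comes back at the next infusion, three times. Table 2 shows no diary collected at the initial visit. Sections 9 and 13 give the ways a series can end early:

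- "The participants are free to withdraw at any time".
- A participant who stops communicating, or whose oncologist takes them off the qualifying chemotherapy, counts as lost to follow-up.
- A participant with essential-oil sensitivity is withdrawn from the study. This route exists in the intervention arm only.

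**The concern.** The method carries its own rule for incomplete data. A between/within ANOVA on three repeated measures needs all three values from each participant, and SPSS removes anyone who lacks one. Someone who returned the first two diaries and then left contributes nothing, although two thirds of their data are in hand.

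Two things are at stake. The first is power, in a trial of 100 whose size is given without derivation or attrition margin. The second is bias: if those who leave differ in antiemetic use from those who stay, the arms are compared among selected participants. A likelihood-based mixed model on the same data, in the same software, avoids the automatic deletion.

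**Working it through.** **Inputs from the documents.** Total sample 100 (sections 6 and 24); three diary time points and SPSS 26 (section 11); "A type I error rate of .05 will be used to determine significance for all analyses".

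**Inputs assumed, because the documents are silent.** 50 per arm; two-sided test; unit SD; equal correlation ρ = 0.5 between visits (range 0.3 to 0.7); an effect giving 80% power on full data; loss rate m of 5%, 10% or 15%. The plan states no power, effect size or dropout rate, so it has no figure to reproduce.

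**Step 1: which procedure.** A sphericity test and a Greenhouse-Geisser correction belong to the repeated-measures general linear model. A likelihood mixed model with its own covariance structure has no use for either. Mixed ANOVA is therefore the procedure with listwise deletion.

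**Step 2: participants kept.** Two patterns of loss are considered: each diary missing independently with probability m, or permanent dropout with probability m before each of the three collections. Both give a complete fraction of (1 − m)³:

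- 0.95³ = 0.857, so 14% are discarded.
- 0.90³ = 0.729, so 27% are discarded.
- 0.85³ = 0.614, so 39% are discarded.

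At m = 10%, complete cases supply 3 × 72.9 = 218.7 diaries. Under independent loss 270 are returned, so about 51 go unused. Under dropout 90 + 81 + 72.9 = 243.9 are returned, so about 25 go unused.

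**Step 3: power for the arm effect averaged over visits.** The variance of a participant's three-visit mean is (1 + 2ρ)/3 = 0.667. The full-data standard error is √(2 × 0.667/50) = 0.163, so the effect giving 80% power is 2.80 × 0.163 = 0.46 SD. Complete-case power is Φ(2.80 × √((1 − m)³) − 1.96). At 10% this is Φ(2.39 − 1.96) = Φ(0.43) = 0.667.

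For the mixed model, the information n × w × S⁻¹ is summed over the missingness patterns. Here w is the pattern's probability and S the correlation matrix of the observed visits. The sum is inverted and the three visits averaged with equal weight.

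| m | Mixed ANOVA, either pattern | Mixed model, independent loss (ρ 0.3-0.7) | Mixed model, permanent dropout (ρ 0.3-0.7) |
|---|---|---|---|
| 5% | 73.7% | 79.3% (78.9-79.6) | 77.0% (76.6-77.4) |
| 10% | 66.7% | 78.5% (77.6-79.2) | 73.7% (72.7-74.5) |
| 15% | 59.3% | 77.6% (76.3-78.6) | 70.0% (68.5-71.4) |

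**Step 4: bias, as an illustration.** Take a true difference of −0.40 SD and ρ = 0.5. Let later diaries be missing with probability 0.40 if Visit 1 use exceeds 0.5 SD above the control mean, and 0.05 otherwise.

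- *Controls.* The fraction kept is 0.60 × 0.3085 + 0.95 × 0.6915 = 0.842. The Visit 1 mean shifts by (0.60 − 0.95) × φ(0.5)/0.842 = −0.35 × 0.352/0.842 = −0.146. The three-visit mean shifts by (1 + 0.5 + 0.5)/3 = 2/3 of that, −0.098.
- *Aromatherapy, same rule.* The threshold is now 0.9 SD above the arm's own mean. The fraction kept is 0.60 × 0.184 + 0.95 × 0.816 = 0.886, and the shift is 2/3 × (−0.35 × 0.266/0.886) = −0.070. The estimated difference is −0.470 + 0.098 = **−0.37**.
- *Aromatherapy, with 0.10 in place of 0.40.* The fraction kept is 0.90 × 0.184 + 0.95 × 0.816 = 0.941, and the shift is 2/3 × (−0.05 × 0.266/0.941) = −0.009. The estimated difference is −0.409 + 0.098 = **−0.31**.

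The shrinkage is about 7% when the arms share a mechanism and about 22% when they do not.

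**The case against.** The strongest reply is that the loss may be small and the gain smaller. Several parts of that stand.

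- *Holds and admissions.* A reader might count these as lost diaries, since section 8 speaks of a participant who "has their chemotherapy temporally held during their study period". The same sentence postpones the study procedures to the next outpatient visit, and section 9 repeats this. On the documents they delay collection and do not by themselves lose a diary. The point rests on withdrawal, loss to follow-up and unreturned packets.
- *Pattern of loss.* A reader might infer that a mixed model keeps power near 78% whatever happens. That needs diaries to go missing independently of one another. Apart from unreturned packets, the routes in the documents are permanent exits, for which the last column of the table is the fairer guide. Someone who leaves before returning any diary is lost to both methods.
- *Bias.* A reader might infer a large bias, for example −0.29 SD against a true −0.46 if dropout follows recent use in controls only. No passage describes that mechanism, and the one arm-specific exit, oil sensitivity, is in the other arm. Nor does deletion always bias the result: with no true effect and the same mechanism in both arms, the complete-case difference is unbiased even though dropout depends on use.
- *Reach.* The CINV analysis is a logistic regression, which this point does not touch. The Study Endpoints section lists antiemetic use as secondary, while section 11 treats it as primary. The two should be reconciled, but the deletion rule is the same either way.

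None of this rescues the chosen method. In both patterns in the table it has lower power than the alternative, and it has no advantage that offsets this.

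**Conclusion.** The point holds at moderate size. The named procedure discards any participant without all three diaries, and nothing in the supplied text compensates. Over an assumed loss of 5% to 15%, the mixed model's gain is about 6 to 18 percentage points of power if diaries go missing independently (79.3 − 73.7; 77.6 − 59.3). Under permanent dropout it is about 3 to 11 points (77.0 − 73.7; 70.0 − 59.3). If every diary came back, there would be no effect.

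Bias is a possibility, not a demonstrated result: modest if dropout depends on earlier use in the same way in both arms, larger if the dependence differs by arm. The deletion itself follows from the method and software named. The sizes rest on the stated assumptions, since the documents give no missingness rate, effect size or power target.

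**What to change.** In section 11, replace the Mixed ANOVA for antiemetic use with a linear mixed model (SPSS MIXED, REML) with arm, visit and arm-by-visit terms and an unstructured within-participant covariance. Include every randomised participant with at least one diary, analysed in the randomised arm. Remove the sphericity test and the Greenhouse-Geisser step, which no longer apply.

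Add a sensitivity analysis for missing data, for instance one that shifts the unobserved values over a stated range, separately by arm. It is needed because the model is valid only under missing at random, and stopping chemotherapy or leaving for oil sensitivity may be related to unrecorded use. State also how many participants return no diary, since the model cannot use them.

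The same replacement can serve resilience, distress and quality of life, where the Mixed ANOVA drops anyone without a final visit. The gain there is smaller, because a participant with only a baseline value says little about change.

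The cost is SAP wording and one extra analysis, with the same software and data. The price is reliance on missing at random, which the sensitivity analysis is there to probe.
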